6.3.4.1 Photographic Documentation of Injection Site

The investigator should photograph the injection site (abdomen or buttock, as applicable) at the time the injection is given. This is to provide a pre-reaction/baseline photograph in the event that a reaction does occur.

If a visible ISR (i.e. one that could be observed in a photograph) subsequently develops, a digital photograph of the injection site will be taken by the investigator. The picture must be uploaded into the eCRF. Prior to the photograph being taken, a label will be placed close to the injection site. This label will display a centimetre ruler and contain space for the entry of participant number, visit number, date of visit and time of photograph. The photograph must be taken with the camera at an angle 90 degrees perpendicular to the injection site wherever possible. The details regarding the instructions for taking the photograph will be documented in the photography manual.

ISRs at the abdominal site should be monitored and photographed at each study visit until complete absence/resolution. ISRs at the buttock site should be monitored and photographed at each study visit until Day 42 or until complete absence/resolution, whichever is later.

6.3.5 Safety Laboratory Variables

Fasted (≥8 hours) blood samples for haematology and biochemistry tests, as well as a urine sample for urinalysis, will be collected for safety monitoring at screening, baseline, Day 28, all dosing visits of Stage 2 and the follow-up visit. For safety analysis, a blood volume of approximately 8 mL will be drawn per timepoint. Full details of blood volumes drawn during

^a In addition to grading the measured local reaction at the greatest single diameter, the measurement should be recorded as a continuous variable.

^b Swelling should be evaluated and graded using the functional scale as well as the actual measurement.

the study are documented in the Laboratory Manual. An overview of measured parameters is given in Table 11.

Table 11: Clinical Safety Laboratory Tests

Table 11. Chin	cal Safety Laboratory Tests		
Haematology:	Haemoglobin	Biochemistry:	Alkaline phosphatase
	Erythrocytes		ASAT
	Leucocytes		ALAT
	Thrombocytes		■-GT
	Neutrophils		Creatinine
	Eosinophils		Fasting glucose
	Basophils		Fasting insulin
	Lymphocytes		Urea
	Monocytes		Total Bilirubin
Urinalysis:	Leucocytes		Total protein
	Erythrocytes		Sodium
	Epithelial cells		Potassium
	рH		Total cholesterol
	Protein		LDL
	Glucose		HDL
	Urobilinogen		VLDL
	Ketones		Triglycerides
	Bilirubin		HbA1c (screening visit only)
	Nitrite		
	Specific density		

ALAT=alanine aminotransferase; ASAT=aspartate aminotransferase; HDL=high-density lipoprotein; LDL=low-density lipoprotein; VLDL=very low-density lipoprotein; ■-GT=gamma-glutamyl transpeptidase

6.3.6 Additional Safety Assessments

It will be left to the investigators' discretion to perform safety assessments in addition to those outlined above. Unless useful for specific purposes (e.g. individual SAEs), the data from these additional safety assessments will not form part of the database of the present study.

6.3.7 Adverse Events

All AEs, including intercurrent illnesses or pathological changes in laboratory values, must be reported and documented in detail including the time of start and end of onset and the outcome. The measures taken will be documented in the eCRF as well as intensity, relationship to study medication and seriousness of the AE.

6.3.7.1 **Definition of Adverse Events**

An AE is any untoward medical occurrence in a participant or clinical investigation participant who is administered a pharmaceutical product. This untoward medical occurrence does not necessarily have a causal relationship with the administered treatment. An AE can, therefore, be defined as any unfavourable and unintended sign (including abnormal laboratory findings), symptom, or disease that is temporally associated with the use of a medicinal (investigational) product, whether or not related to that medicinal (investigational) product. If, during treatment with an investigational product, pathological laboratory values occur which were not present before the treatment started, further clinical or laboratory tests must be

carried out until the values return to the normal range or until a plausible explanation is found (e.g. concomitant disease) for the change in the laboratory values.

Symptoms or clinically significant laboratory or instrumental (e.g. electrocardiographic) abnormalities of a pre-existing condition, such as cancer or other diseases, should not be considered an AE. However, occurrence of new symptoms, laboratory, or instrumental abnormalities, as well as worsening of pre-existing ones, are considered AEs.

Laboratory values outside the normal laboratory-specific reference range, which make an intervention necessary and/or are considered clinically significant by the investigator must be reported as AEs. If the abnormal laboratory value is a sign of a disease, only this diagnosis should be reported as an AE.

An AE is considered to be an adverse drug reaction (ADR) if a causal relationship between a medicinal product and an AE is at least a reasonable possibility.

6.3.7.2 Assessment of Adverse Events

The investigator will identify the occurrence of pre-dose events and/or AEs through non-leading questioning and examination of the participant.

For each AE, the investigator will document the following:

- **Signs and symptoms** of the event (if a specific disease can be diagnosed, this disease should be the reported AE; if only signs and symptoms can be evaluated, each sign or symptom should be reported as a separate AE)
- Onset date and time (if a change from pre-dose in a laboratory test is reported as an AE, the start date is the date of collection of the first laboratory sample that shows the change)
- End date and time (if a change from pre-dose in a laboratory test is reported as an AE, the end date is the date of collection of the first laboratory sample that shows a return to pre-dose level)
- Measure taken (none, drug treatment required, hospitalisation or prolonged hospitalisation, study discontinuation, other measures [specification])
- **Outcome** (recovered/resolved, recovering/resolving, recovered/resolved with sequelae, not recovered/not resolved, fatal, unknown)

In addition, each AE will be rated by the investigator according to the following categories (the Sponsor has to carry out a separate assessment for causal relationship, seriousness, and expectedness):

Relationship to Study Medication

If the AE is a deterioration in the study disease and, therefore, indicates a lack of efficacy of the study medication, the causality assessment "no relationship" will be made, as the impairment of health is not caused by a intolerability of the study medication. "Deterioration of study disease" is to be given as the cause of the AE.

Assessments of relationship to study medication will be made by the investigator first. For the evaluation of the relationship between AEs and IMP the following definitions will be used:

Related

This category applies to those AEs which the investigator feels are incontrovertibly related to the IMP. The relationship between the IMP and an AE is considered definite if the AE:

- follows a reasonable temporal sequence after administration of the IMP or after achieving effective levels in body fluids and tissues, respectively
- is already known as side effect in relation to the IMP
- disappears or decreases on cessation of the IMP
- recurs with re-exposure to the IMP

Probable

This category applies to those AEs which, after careful medical consideration at the time they are evaluated, are felt with a high degree of certainty by the investigator to be related to the IMP. The relationship between the IMP and an AE is considered probable if the AE:

- follows a reasonable temporal sequence after administration of the IMP
- has already been described as a side effect of the IMP
- disappears or decreases on cessation of the IMP
- cannot be reasonably explained by the participant's clinical state

Possible

This category applies to those AEs for which, after careful medical consideration at the time they are evaluated, a connection with the IMP appears improbable but cannot be ruled out with certainty. The relationship between the IMP and an AE is considered possible if the AE:

- follows a reasonable temporal sequence after administration of the IMP
- has already been described as an AE in connection with the IMP
- could also be reasonably explained by a number of other causes

Unlikely

In general, this category can be considered applicable to those AEs which, after careful medical consideration at the time they are evaluated, are judged with a high degree of certainty to be unrelated to the IMP. The relationship between the IMP and an AE is considered unlikely if the AE:

- does not follow a reasonable temporal sequence after administration of the **IMP**
- could also be reasonably explained by a number of other causes
- does not follow a known pattern of response to the IMP

Not related

This category applies to those AEs which, after careful consideration, are clearly and incontrovertibly due to causes other than the IMP (intercurrent disease, worsening of study indication/lack of efficacy, concomitant disease, concomitant therapy, other).

Intensity

Regardless of the classification of an AE as serious or non-serious (see below), its intensity must be assessed according to medical criteria alone using the Common Terminology Criteria for Adverse Events (CTCAE) classification (v5.0):

Grade 1 (mild): asymptomatic or mild symptoms; clinical or diagnostic

observations only; intervention not indicated

minimal, local or non-invasive intervention indicated; limiting **Grade 2 (moderate):**

> age-appropriate instrumental activities of daily living (e.g. preparing meals, shopping, using the telephone, managing

money, etc.)

Grade 3 (severe): severe or medically significant but not immediately life-

threatening; hospitalisation or prolongation of hospitalisation indicated; disabling; limiting self-care activities of daily living (e.g. bathing, dressing, undressing feeding self, using toilet,

taking medications, and not bedridden, etc.)

Grade 4 (life-threatening): life-threatening consequences; urgent intervention indicated Grade 5 (death): death related to AE (death is reported as an outcome of an AE)

It should be noted that a severe AE does not necessarily have to be serious in nature and that a serious AE need not be severe.

Seriousness

An SAE is an untoward medical occurrence that at any dose:

- results in death
- is life-threatening
- requires in-participant hospitalisation or prolongation of existing hospitalisation
- results in persistent or significant disability/incapacity
- is a congenital anomaly or birth defect

or

• is an important medical event that does not have to be immediately life-threatening or result in death or hospitalisation, but which may jeopardise the participant or may require medical intervention to prevent 1 of the outcomes listed above.

All SAEs must be reported immediately (within 1 working day) to the drug safety department at IntuVigilance Limited, by the investigator.

All AEs that do not fall into any of the above categories are defined as non-serious.

Expectedness

At the drug safety department at IntuVigilance Limited an additional rating for expectedness of AEs will be given:

Expected: The event is judged expected if its description agrees in nature, severity,

frequency, and specificity with the description of events in the Investigator's

Brochure.

Unexpected: SAEs which do not fall into the expected category are assessed to be

unexpected.

A suspected unexpected serious adverse drug reaction (SUSAR) is defined as an untoward and unintended response to an IMP, which is not listed in the applicable product information, and meets 1 of the above-mentioned serious criteria. The drug safety department at IntuVigilance Limited, acting on behalf of the Sponsor, will ensure that all SUSARs associated with the IMP will be reported to the applicable regulatory authority/competent authorities and the relevant independent ethics committees(IECs)/IRBs in accordance with the applicable national/local regulations (usually within 7 calendar days for life-threatening and fatal SUSARs or within 15 calendar days for all other SUSARs). The drug safety department at IntuVigilance Limited will also promptly notify all investigators about any SUSAR.

6.3.7.3 Follow-up of Adverse Events

Regardless of the duration of the study, each AE must be followed-up until it subsides or until the cause is known or an adequate final assessment can be given. The maximum follow-up period will be 6 weeks after the participant's study termination. If after 6 weeks no final outcome can be acquired, the outcome of the AE is 'unresolved'.

6.3.7.4 Documentation and Reporting of Adverse Events

Any AE has to be documented in the eCRF with the specifications made in Section 6.3.7.2. All SAEs must be reported immediately (within 1 working day) to the drug safety manager or the responsible person and/or the clinical research associate (CRA) by the investigator (see Responsibilities).

All SAEs must be reported by the investigator immediately (within 24 hours) to the drug safety department at IntuVigilance Limited via the eCRF (see below).

A specific SAE form for immediate reporting will be provided to the investigators as part of the eCRF. In case of a SAE, this form should be completed and checked immediately within the eCRF. These data entries will be used to automatically create the corresponding SAE reporting form. Furthermore, any other requested data (like concomitant medications) already present in the eCRF will be used to populate the respective fields of the SAE reporting form. A trigger mechanism implemented in the eCRF will ensure that the form will be sent automatically via email to the drug safety department at IntuVigilance Limited within 24 hours.

Note: Any changes in fields being part of these reports will create a new (follow-up) report, which will also be sent automatically.

If due to any reason the electronic completion and forwarding of the SAE reporting form via the eCRF is not possible, the investigator may fill out the pre-printed Sponsor SAE reporting form manually and send the required information via scanned email to both parties mentioned above (see Responsibilities for contact details).

Follow-up reports will be provided by the investigator each time new information on the SAE becomes available (until the case is solved or the participant has recovered). For reporting of follow-up information, a similar procedure as for reporting of initial SAEs will apply. Notification to the regulatory authorities, the IECs, and the investigator sites about all SUSARs will be performed by and to the investigator sites and/or by the investigator (as applicable) according to all applicable national/local regulations.

6.4 Pharmacokinetics

6.4.1 Pharmacokinetic Variables

Pharmacokinetic parameters will be generated using Phoenix WinNonlin Version 6.4 or higher for evaluation.

The concentrations of all participants who successfully complete the study will be analysed and samples of withdrawn or dropout participants will not be analysed. This analysis may include the parameters shown in Table 12. Full details will be presented in the statistical analysis plan (SAP).

Table 12: Pharmacokinetic Parameters

PK	Description	Unit
Parameter		
AUC _{0-t}	Area under the concentration-time-curve from time zero up to	ng•h/
	the last measurable concentration at timepoint t	mL
AUC_{0-t1}	Area under the concentration-time-curve from time zero up to	ng•h/
	concentration at timepoint t1 after which the concentrations start	mL
	to rise again towards a second peak, t1 will be determined after	
	review of the concentration-time profiles (immediate release	
	component of total observed AUC)	

PK	Description	Unit
Parameter	-	
AUC _{t1-t}	Area under the concentration-time-curve from timepoint t1 up to	ng•h/
	timepoint t (slow release component of total observed AUC)	mL
$\mathrm{AUC}_{0\text{-}\infty}$	Area under the concentration-time-curve from time zero up to	ng•h/
	infinity (∞)	mL
C_{max}	Maximum plasma concentration	ng/mL
$C_{max,0-t1}$	Maximum plasma concentration after administration from zero up to timepoint t1	ng/mL
C _{max,t1-t}	Maximum plasma concentration after administration from timepoint t1 up to timepoint t	ng/mL
T_{max}	Time to reach C_{max} after dosing	h
$T_{max,0-t1}$	Time to reach $C_{max,0-t1}$ after dosing	h
T _{max,t1-t}	Time to reach $C_{max,t1-t}$ after dosing	h
$\lambda \mathbf{z}$	Apparent terminal rate constant	1/h
t ½	Apparent terminal plasma half-life	h

h=hours; PK=pharmacokinetic

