6.4.2 Blood Sampling Time Points, Handling and Labelling of Blood Samples

Blood samples for PK evaluation will be collected by venepuncture (or by using an indwelling catheter). A blood volume of 5 mL will be drawn per timepoint.

Blood is drawn for PK analysis according to the schedule below, where timepoints are relative to IM injection of teverelix TFA at time zero, and the pre-dose PK sample is collected within 30 minutes prior to IM injection (Table 13).

Handling and labelling of blood samples for PK analysis will be performed according to the instructions provided by the central analytical laboratory. Special tubes, labels, packaging, and instructions for storage and shipment will also be provided by the analytical laboratory. Blood samples should be shipped for analysis on the day of collection.

Blood teverelix TFA concentrations will be determined from all collected samples using a validated sensitive analytical procedure (e.g. inductively coupled plasma mass spectrometry) at a specialised central analytical laboratory.

After completion of all analyses, any leftover blood or blood samples will be destroyed immediately after termination of the study.

Stability data supports the storage of teverelix PK samples:

- In a freezer set at nominally -20°C for up to 376 days
- In a freezer set at nominally -80°C for up to 60 days

Table 13: Pharmacokinetic Timepoints

Timepoi	Pre-	1	1.5	2	2.5	3	4	8	12	18	24	48	72
nt	dose	h	h	h	h	h	h	h	h	h	h ^a	h	h
Window	±0	±1	±1	±15	±15	±15	±15	±15	±15	±15	±15	±1	±1
	day	5	5	min	hou	hou							
		mi	mi									r	r
		n	n										
	•	•	•	•	•	•	•	•	•	•	•	•	•

Timepoin t	Da y 4 ^b	Da y 7 ^b	Da y 10 ^b	Da y 12 ^b	Da y 14 ^b	Da y 21 ^b	Day 28°	Day 35	Thereafter at each dosing visit and follow up visits ^d
Window	±0	±0	±1	±1	±1	±1	±3	±3	±3 days
	day	day	day	day	day	day	day	day	
							S	S	
	•	•	•	•	•	•	•	•	•

PK=pharmacokinetic

6.5 **Pharmacodynamics**

The following parameters will be investigated:

- T
- LH
- FSH
- PSA

^a Participants will remain in the clinic as in-participants until after the 24-hour PK blood sample has been drawn after which time they will be discharged.

^b From Day 4 onwards, when a PK sample is to be drawn on a non-dosing day, the PK sample should be drawn at the same time of day as the Day 0 pre-dose PK sample was drawn (+ 1 hour).

^c Before dosing (up to 30 minutes pre-dose). Dosing should be done at the same time of day throughout the study (or at least + 1 hour of this timepoint).

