#### **3.6 Pharmacokinetic (PK) Analysis Set**

The PK Analysis Set is defined as the subset of the Per protocol (PP) analysis set providing analysable samples to assess the pharmacokinetics of the active substance.

A PK profile for a subject may be excluded from the PK Analysis Set in the relevant period/on that sampling occasion if the subject:

---

Document:

C:\ProgramData\activePDF\Temp\DocConverter\API\Input\\$651f4dc0b253\$FE3041C5883446E892B20AB6D3F0E1BD.docx

Author: [name]

Version and Date: Version 1.0, 21 Apr 2023

Page 28 of 66

- did not receive active treatment (e.g. excluding samples taken pre-dose and following administration with Placebo) or the correct dose.
- did not provide analysable samples at more than 50% of planned time points in the PK profile (e.g. due to drop out or laboratory errors).

All PK analyses will be performed on the PK Analysis Set.

In addition, PK data may be flagged to be excluded from specific summaries if, for example, the derived parameters are considered unreliable.

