#### 4.3.8.1 Pharmacokinetic variables

Pharmacokinetic parameters will be generated using Phoenix WinNonlin Version 8.1 or higher for evaluation [1].

Data from participants who have sufficient concentrations to derive at least one PK parameter will be analysed. This analysis will include the parameters shown in **Error! Reference source not found..**

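### The protocol and SAP contradict each other on who enters the PK analysis, and two of the four rules would exclude men withdrawn for testosterone above 2 ng/mL

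*Protocol*

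**What the plan says.** Four places set a rule for which men or samples count.

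- **Protocol 6.4.1:** "The concentrations of all participants who successfully complete the study will be analysed", and "samples of withdrawn or dropout participants will not be analysed".
- **Protocol 6.4.2:** "Blood teverelix TFA concentrations will be determined from all collected samples".
- **SAP 3.6:** "The PK Analysis Set is defined as the subset of the Per protocol (PP) analysis set providing analysable samples". The section applies this set to every PK analysis. SAP 3.7 admits to the per-protocol (PP) set only ITT participants who complete the study without a major violation. SAP 3.6 also allows a profile to be dropped if the subject "did not provide analysable samples at more than 50% of planned time points in the PK profile", and gives drop-out as one example of a cause.
- **SAP 4.3.8.1:** "Data from participants who have sufficient concentrations to derive at least one PK parameter will be analysed". Its stated grounds for leaving out a profile are lack of active treatment and too little concentration data. Completion is not a condition.

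SAP 3.1 and 4.3.8 add that a separate PK SAP is planned, based on the PK Analysis Set, and that the set as given in this SAP is informational and not used for any analysis in it. SAP 7.1 does not list the PK data rule among the changes from the protocol.

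**The concern.** These rules cannot all be followed, and the difference between them depends on outcome. Protocol 4.3 and 5.5 make withdrawal mandatory when local T exceeds 2 ng/mL, and Protocol 3.1 counts those men as treatment failures. A rule that requires completion therefore removes treatment failures, as the protocol defines them, from the PK results.

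Describing the PK profile is a study objective, and Protocol 8.1.12 says the Group 2 data are to support dose selection for Phase 3. Protocol 3.2 itself attributes the more sustained T suppression by the subcutaneous route to better maintained systemic levels, so low exposure in some failures is a reasonable hypothesis. A completers-only PK set could not examine it. If the samples are not assayed at all, any withdrawn men in the 30-subject Holter subset would also be lost to the concentration-QTc modelling described in Protocol 6.3.4.

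**Working it through.** **1. Which rules exclude a man withdrawn for T above 2 ng/mL?**

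| Rule | Is he included? |
|---|---|
| Protocol 6.4.1 | No: not a completer |
| Protocol 6.4.2 | His samples are assayed |
| SAP 3.6 with 3.7 | No: not in the PP set |
| SAP 4.3.8.1 | Yes, if one parameter is derivable |

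**2. Would he be excluded anyway for too little data?** Counts are from Protocol Table 13 (PK timepoints) and the visit schedule.

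- Pre-dose, 1, 1.5, 2, 2.5, 3, 4, 8, 12, 18, 24, 48 and 72 h: 13 samples.
- Days 4, 7, 10, 12, 14 and 21: 6 samples. Total by Day 21: 13 + 6 = 19.
- Days 28, 35 and 42 precede the first maintenance dose, because the Day 42 sample is taken before dosing. Planned up to that dose: 19 + 3 = 22, so 19/22 = 86% exist by Day 21.
- Whole study without Stage 3: 22 + Days 84, 126 and 168 + follow-up = 26, and 19/26 = 73%.
- Whole study with Stage 3: 25 through Day 168 + 8 visits (Days 203 to 252) + final assessment = 34, and 19/34 = 56%.

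He passes the SAP 3.6 criterion of more than 50% against any of these denominators. A sample at the Day 28 visit would make it 20. Only the completion condition removes him.

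**3. How large could the effect be?** The documents report no exposure by response, so this is a range under assumptions. Let f be the fraction excluded and k the excluded men's mean exposure as a fraction of completers' mean exposure. Then

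overstatement = 1/[(1 − f) + f·k] − 1.

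Illustrative values of f:

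- 6/60 is the largest Group 2 failure count that does not trigger the stop at 7 (Protocol 3.1).
- 10/60 is the planned dropout. Protocol 8.1.12 reproduces: 50/(1 − 0.16) = 59.5, so 60 enrolled and 60 − 50 = 10 not evaluable.
- 3/24 is the Group 1 failure trigger over planned enrolment.

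| Excluded | k = 0.25 | k = 0.50 | k = 0.75 | k = 1 |
|---|---|---|---|---|
| 6/60 | 8.1% | 5.3% | 2.6% | 0 |
| 10/60 | 14.3% | 9.1% | 4.3% | 0 |
| 3/24 | 10.3% | 6.7% | 3.2% | 0 |

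Example: f = 0.10, k = 0.25 gives 1/(0.90 + 0.025) − 1 = 1/0.925 − 1 = 8.1%.

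**The case against.** A reader might infer that exposure in treatment failures will be unknown and that the exposure results are biased upward. The documents do not support that as a settled fact, for these reasons.

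- **Two of the four rules point the other way.** Protocol 6.4.1 also leaves full details to the SAP, and SAP 4.3.8.1 has no completion condition. The drop-out example in SAP 3.6 would be largely redundant if every drop-out were already excluded.
- **The operative rule may sit in the PK SAP**, which is not among the documents. This lowers confidence but does not remove the problem: that plan is to be based on the same PP-nested set, so the restriction carries over unless someone changes it.
- **The direction of any bias is not shown.** Lower exposure in failures is plausible but undocumented, and equal exposure gives no bias. The only exposure-response modelling these documents name is concentration-QTc. The move from Group 1 to Group 2 and the Group 2 sample size rest on testosterone response, not on the PK set.
- **Not every efficacy failure is lost.** Men with T of 0.5 to 2 ng/mL miss the castration threshold but continue, and can be in the PK set.
- **The Day 21 profile is not the full loading-dose profile.** The three missing samples fall late and bear on the terminal phase of a depot product.
- **The counts are assumptions.** Nothing says that the 16% dropout includes men withdrawn for T above 2 ng/mL. Six is not a firm ceiling either, because failures can still accrue after enrolment stops.

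All of this stands as a limit on the claim. None of it reconciles the four rules, or gives a data-adequacy reason for removing men who meet the SAP's own sampling criterion.

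**Conclusion.** The contradiction is real and should be resolved. Under Protocol 6.4.1, or under SAP 3.6 with 3.7, men withdrawn for local T above 2 ng/mL are excluded on outcome even though they can have 19 of 22 pre-maintenance samples. Under Protocol 6.4.2 and SAP 4.3.8.1 they are kept. Which rule will operate cannot be determined from these documents.

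If a restrictive rule is applied, exposure summaries could be unrepresentative of all treated men. Assuming that excluded men have 25% to 75% of completers' exposure, the overstatement of mean exposure is about 3% to 8% at 6/60 and 4% to 14% at 10/60. It is zero if exposure is equal. The primary endpoint and the adaptive decision are not affected.

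**What to change.** - Remove the sentence in Protocol 6.4.1 that excludes samples of withdrawn participants, and the completers-only condition joined to it.
- Define the PK set as all dosed participants with at least one evaluable post-dose concentration, regardless of completion or PP membership. Report each parameter only where it is estimable; terminal-phase parameters may not be for early withdrawals.
- Use the same definition in SAP 3.6, SAP 4.3.8.1 and the PK SAP, and list the change in SAP 7.1.
- Assay all collected samples, as Protocol 6.4.2 already states. Do so within the stability limits given there (376 days at −20°C, 60 days at −80°C) and before leftover samples are destroyed at study termination.
- Summarise exposure separately for men withdrawn for T above 2 ng/mL.

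The cost is a formal protocol amendment for wording (Protocol 10.2), matching SAP edits, assay of samples already drawn, and some incomplete profiles in the listings. Any samples already held beyond the stability limits would need to be flagged, since late assay may not be supported.
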